4.4 Diabetes	

Definition: T2DM is a combination of insulin resistance and insufficiency that may require oral or insulin therapy. It may be new onset or exacerbated during therapy for nonimmunologic reasons, such as corticosteroid exposure.
 
Autoimmune T1DM results from islet cell destruction and is often acute onset, with ketosis and an insulin requirement
 
Diagnostic work-up
 
Monitor patients for hyperglycemia or other signs and symptoms of new or worsening DM, including measuring glucose at baseline and with each treatment cycle during induction for 12 weeks, then every 3-6 weeks thereafter. To guide the work-up in new-onset hyperglycemia, clinicians should consider a patient's medical background, exposure history, and risk factors for each subtype of DM.
	

4.0 Endocrine Toxicity	
Laboratory evaluation in suspected T1DM should include testing for ketosis in urine and an assessment of the anion gap on a metabolic panel. Anti–glutamic acid decarboxylase, anti–islet cell, or anti–insulin antibodies are highly specific for autoimmune diabetes. Insulin and C-peptide levels can also assist in the diagnosis.	
Grading	Management
G1: Asymptomatic or mild symptoms; fasting glucose value > ULN (160 mg/dL); fasting glucose value > ULN (8.9 mmol/L); no evidence of ketosis or laboratory evidence of T1DM	Can continue ICPI with close clinical follow-up and laboratory evaluation May initiate oral therapy for those with new-onset T2DM Screen for T1DM if appropriate, for example, acute onset with prior normal values or clinical concern for ketosis
G2: Moderate symptoms, able to perform ADL, fasting glucose value > 160-250 mg/dL; fasting glucose value > 8.9-13.9 mmol/L, ketosis or evidence of T1DM at any glucose level	May hold ICPI until glucose control is obtained Titrate oral therapy or add insulin for worsening control in T2DM Should administer insulin for T1DM (or as default therapy if there is confusion about type) Urgent endocrine consultation for any patient with T1DM; in the absence of endocrinology, internal medicine may suffice Consider admission for T1DM if early outpatient evaluation is not available or signs of ketoacidosis are present
G3-4: Severe symptoms, medically significant or life-threatening consequences, unable to perform ADL G3: > 250-500 mg/dL (> 13.9-27.8 mmol/L) G4: > 500 mg/dL (> 27.8 mmol/L)	Hold ICPI until glucose control is obtained on therapy with reduction of toxicity to G1 or less Urgent endocrine consultation for all patients Initiate insulin therapy for all patients Admit for inpatient management: Concerns for developing DKA, Symptomatic patients regardless of diabetes type, New-onset T1DM unable to see endocrinology

Additional considerations
 
Insulin therapy can be used as the default in any case with hyperglycemia
 
Long-acting therapy alone is not usually sufficient for T1DM, where half of daily requirements are usually given in divided doses as prandial coverage and half as long acting.
 
Insulin doses will be lower in T1DM because of preserved sensitivity (total daily requirement can be estimated at 0.3-0.4 units/kg/d).
 
In T2DM, sliding-scale coverage with meals over a few days provides data to estimate a patient’s daily requirements and can be used to more rapidly titrate basal needs.
 
All recommendations are expert consensus based, with benefits outweighing harms, and strength of recommendations are moderate.
	

Abbreviations: ACTH, adrenocorticotropic hormone; ADL, activities of daily living; CT, computed tomography; DKA, diabetic ketoacidosis; DM, diabetes mellitus; EMS, emergency medical services; FSH, follicle-stimulating hormone; FT4, free thyroxine; G, Grade; ICPI, immune checkpoint inhibitor; irAE, immune-related adverse event; LH, luteinizing hormone; MRI, magnetic resonance imaging; PTU, propylthiouracil; 2L, second-line; SSKI, potassium iodide; T1DM, type 1 diabetes mellitus; T2DM, type 2 diabetes mellitus; TRAb, thyroid-stimulating hormone receptor antibody; TSH, thyroid-stimulating hormone; TSI, thyroid-stimulating immunoglobulin; ULN, upper limit of normal.

Table A5 Management of Musculoskeletal irAEs in Patients Treated With ICPis

5.0 Musculoskeletal Toxicities	
5.1 Inflammatory arthritis	

Definition: A disorder characterized by inflammation of the joints
 
Clinical symptoms: Joint pain accompanied by joint swelling; inflammatory symptoms, such as stiffness after inactivity or in the morning, lasting > 30 minutes to 1 hour; improvement of symptoms with NSAIDs or corticosteroids but not with opioids or other pain medications may also be suggestive of inflammatory arthritis.
	

Diagnostic work-up
 
G1
 
Complete rheumatologic history and examination of all peripheral joints for tenderness, swelling, and range of motion; examination of the spine Consider plain x-ray/imaging to exclude metastases and evaluate joint damage (erosions), if appropriate
 
Consider autoimmune blood panel including ANA, RF, and anti-CCP, and anti-inflammatory markers (ESR and CRP) if symptoms persist; if symptoms are suggestive of reactive arthritis or affect the spine, consider HLA B27 testing
 
G2
 
Complete history and examination as above; laboratory tests as above
 
Consider US ± MRI of affected joints if clinically indicated (e.g., persistent arthritis unresponsive to treatment, suspicion for differential diagnoses such as metastatic lesions or septic arthritis)
 
Consider early referral to a rheumatologist, if there is joint swelling (synovitis) or if symptoms of arthralgia persist > 4 weeks
 
G3-4
 
As for G2
 
Seek rheumatologist advice and review
 
Monitoring: Patients with inflammatory arthritis should be monitored with serial rheumatologic examinations, including inflammatory markers, every 4-6 weeks after treatment is instituted.
	
Grading	Management
All Grades	Clinicians should follow reports of new joint pain to determine whether inflammatory arthritis is present; question whether symptom new since receiving ICPi
G1: Mild pain with inflammation, erythema, or joint swelling	Continue ICPi Initiate analgesia with acetaminophen and/or NSAIDs
G2: Moderate pain associated with signs of inflammation, erythema, or joint swelling, limiting instrumental ADL	Hold ICPi and resume upon symptom control and on prednisone ≤ 10 mg/d Escalate analgesia and consider higher doses of NSAIDs as needed If inadequately controlled, initiate prednisone or prednisolone 10-20 mg/d or equivalent for 4-6 weeks If improvement, slow taper according to response during the next 4-6 weeks; if no improvement after initial 4-6 weeks, treat as G3 If unable to lower corticosteroid dose to < 10 mg/d after 3 months, consider DMARD Consider intra-articular corticosteroid injections for large joints Referral to rheumatology
G3-4: Severe pain associated with signs of inflammation, erythema, or joint swelling; irreversible joint damage; disabling; limiting self-care ADL	For G3: Hold ICPi temporarily and may resume in consultation with rheumatology, if recover to G1 or less For G4: permanently discontinue ICPi Initiate oral prednisone 0.5-1 mg/kg If failure of improvement after 4 weeks or worsening in meantime, consider synthetic or biologic DMARD

5.0 Musculoskeletal Toxicities	
	
Synthetic: methotrexate, leflunomide
 
Biologic: consider anticytokine therapy such as TNF-a or IL-6 receptor inhibitors. (Note: As caution, IL-6 inhibition can cause intestinal perforation; while this is extremely rare, it should not be used in patients with colitis.) Test for viral hepatitis B, C, and latent/active TB test prior to DMARD treatment
 
Referral to rheumatology.

Additional considerations
 
Early recognition is critical to avoid erosive joint damage.
 
Corticosteroids can be used as part of initial therapy in inflammatory arthritis, but due to likely prolonged treatment requirements, physicians should consider starting corticosteroid-sparing agents earlier than one would with other irAEs
 
Oligoarthritis can be treated early on with intra-articular corticosteroids; consider early referral.
 
Consider PCP prophylaxis for patients treated with high dose of corticosteroids for 12 weeks, as per local guidelines.
	
5.2 Myositis	

Definition: A disorder characterized by muscle inflammation with weakness and elevated muscle enzymes (CK). Muscle pain can be present in severe cases. Can be life-threatening if respiratory muscles or myocardium are involved
 
Diagnostic work-up
 
Complete rheumatologic and neurologic history regarding differential diagnosis; rheumatologic and neurologic examination, including muscle strength; and examination of the skin for findings suggestive of dermatomyositis. Muscle weakness is more typical of myositis than pain. Consider pre-existing conditions that can cause similar symptoms.
 
Blood testing to evaluate muscle inflammation
 
CK, transaminases (AST, ALT), LDH, and aldolase can also be elevated
 
Troponin to evaluate myocardial involvement and other cardiac testing, such as echocardiogram, as needed
 
Inflammatory markers (ESR and CRP)
 
Consider EMG, imaging (MRI), and/or biopsy on an individual basis when diagnosis is uncertain and overlap with neurologic syndromes, such as myasthenia gravis, is suspected
 
Consider paraneoplastic autoantibody testing for myositis and neurologic conditions, such as myasthenia gravis
 
Monitoring: CK, ESR, CRP
	

G1: Complete examination and laboratory work-up as above
 
G2: Complete history and examination as above; autoimmune myositis blood panel; EMG, MRI of affected joints
 
Early referral to a rheumatologist or neurologist
 
G3-4: As for G2
 
Urgent referral to a rheumatologist or neurologist
	
Grading	Management
G1: Mild weakness with or without pain	
Continue ICPI
 
If CK is elevated and patient has muscle weakness, may offer oral corticosteroids, and treat as G2
 
Offer analgesia with acetaminophen or NSAIDs if there are no contraindications

G2: Moderate weakness with or without pain, limiting age-appropriate instrumental ADL	
Hold ICPI temporarily and may resume upon symptom control, if CK is normal and prednisone dose 10 mg; if worsens, treat as per G3
 
NSAIDs as needed
 
Referral to rheumatologist or neurologist
 
If CK is elevated three times or more), initiate prednisone or equivalent at 0.5-1 mg/kg

5.0 Musculoskeletal Toxicities	
	May require permanent discontinuation of ICPI in most patients with G2 symptoms and objective findings (elevated enzymes, abnormal EMG, abnormal muscle MRI or biopsy)
G3-4: Severe weakness with or without pain, limiting self-care ADL	For G3: Hold ICPI until G1 or less and permanently discontinue if any evidence of myocardial involvement For G4: permanently discontinue ICPI Consider hospitalization for severe weakness Referral to rheumatologist or neurologist Initiate prednisone 1 mg/kg or equivalent. Consider 1-2 mg/kg of methylprednisolone IV or higher-dose bolus if severe compromise (weakness severely limiting mobility, cardiac, respiratory, dysphagia) Consider plasmapheresis Consider IVIG therapy Consider other immunosuppressant therapy, such as methotrexate, azathioprine, or mycophenolate mofetil, if symptoms and CK levels do not improve or worsen after 4-6 weeks; rituximab is used in primary myositis but caution is advised given its long biologic duration In case of management with rituximab, ICPI treatment should be discontinued
Additional considerations: Caution is advised with rechallenging	

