G2: Asymptomatic (AST or ALT > 3.0 to ≤ 5 x ULN and/or total bilirubin > 1.5 to ≤ 3 x ULN)	
Hold ICPI temporarily and resume if recover to G1 or less on prednisone ≤ 10 mg/d
 
For Grade 2 hepatic toxicity with symptoms, may administer corticosteroid 0.5-1 mg/kg/d prednisone or equivalent if the abnormal elevation persists with significant clinical symptoms in 3-5 days Increase frequency of monitoring to every 3 days
 
Infliximab might not be the most appropriate treatment option in the situation of immune-mediated hepatitis given the potential risk of idiosyncratic liver failure (Note: No clear evidence shows the liver toxicity from infliximab from other studies)
 
In follow-up, may resume ICPI treatment followed by taper only when symptoms improve to G1 or less and corticosteroid ≤ 10 mg/d; taper over at least 1 month
 
Patients should be advised to stop unnecessary medications and any known hepatotoxic drugs

G3: Symptomatic liver dysfunction, fibrosis by biopsy, compensated cirrhosis, reactivation of chronic hepatitis (AST or ALT 5-20 x ULN and/or total bilirubin 3-10x3 ULN)	
Permanently discontinue ICPI
 
Immediately start corticosteroid 1-2 mg/kg methylprednisolone or equivalent
 
If corticosteroid refractory or no improvement after 3 days, consider mycophenolate mofetil or azathioprine (if using azathioprine should test for thiopurine methyltransferase deficiency)
 
Laboratories at daily or every other day; consider inpatient monitoring for patients with AST/ALT > 8 x ULN and/or elevated TB 3 x ULN
 
Increase frequency of monitoring to every 1-2 days

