5.3 Polymyalgia-like syndrome	
Definition: Characterized by marked pain and stiffness in proximal upper and/or lower extremities and no signs of true muscle inflammation such as CK elevation or EMG findings of myositis. No true muscle weakness, difficulty in active motion related to pain Diagnostic work-up	
G1 Complete rheumatologic history regarding differential diagnosis and examination of all joints and skin Check for symptoms of temporal arteritis, such as headache or visual disturbances; refer to ophthalmologist if present, and consider temporal artery biopsy ANA, RF, anti-CCP CK to evaluate differential diagnosis of myositis Inflammatory markers (ESR, CRP) Monitoring: ESR, CRP	
G2: Complete history and examination as above; autoimmune tests as required for differential diagnosis; early referral to a rheumatologist G3-4: As for G2; see rheumatologist advice and review	
Grading	Management
G1: Mild stiffness and pain	Continue ICPI Initiate analgesia with acetaminophen and/or NSAIDs if there are no contraindications
G2: Moderate stiffness and pain, limiting age-appropriate instrumental ADL	Consider holding ICPI and resuming upon symptom control, prednisolone < 10 mg; if worsens, treat as per G3 Initiate prednisone 20 mg/d or equivalent; if symptoms improve, start to taper dose after 3-4 weeks If no improvement or need for higher dosages after 4 weeks, escalate to G3 Consider referral to rheumatology

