10.1 Uveitis/iritis	
Definition: Inflammation of the middle layer of the eye Diagnostic work-up: as per above	
Grading	Management
G1: Asymptomatic	Continue ICPi Refer to ophthalmology within 1 week Artificial tears
G2: Medical intervention required, anterior uveitis	Hold ICPi temporarily until after ophthalmology consult Urgent ophthalmology referral Topical corticosteroids, cycloplegic agents, systemic corticosteroids May resume ICPi treatment once off systemic corticosteroids, which are purely indicated for ocular adverse effects or once corticosteroids for other concurrent systemic irAEs are reduced to ≤ 10 mg; continued topical/ocular corticosteroids are permitted when resuming therapy to manage and minimize local toxicity Re-treat after return to G1 or less
G3: Posterior or panuveitis	Permanently discontinue ICPi Urgent ophthalmology referral. Systemic corticosteroids and intravitreal/periocular/topical corticosteroids
G4: 20/200 or worse	Permanently discontinue ICPi Emergent ophthalmology referral

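### The Grade 3 myositis row lets drug restart at Grade 1 or less without the normal-CK and prednisone 10 mg conditions that the Grade 2 row sets

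*Protocol*

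**What the plan says.** The rules are in Protocol Appendix 5, Table A5, section 5.2.

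- **Grade 1** (mild weakness): drug continues, with one qualification: "If CK is elevated and patient has muscle weakness, may offer oral corticosteroids, and treat as G2".
- **Grade 2** (moderate weakness): drug is held and "may resume upon symptom control, if CK is normal and prednisone dose 10 mg; if worsens, treat as per G3". A comparison sign may have been lost before the 10 mg; I read it as no more than 10 mg/day. The row adds that most Grade 2 patients with objective findings may need to stop permanently.
- **Grade 3** (severe weakness limiting self-care): drug is held "until G1 or less and permanently discontinue if any evidence of myocardial involvement". Prednisone starts at 1 mg/kg, and the row asks for referral to a rheumatologist or neurologist. Drug stops if rituximab is used. CK appears only as a trigger for further immunosuppression.
- **Grade 4**: drug stops permanently.

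The section closes with a general warning about rechallenge. Protocol Section 6.9.2 lists myositis among the important identified risks and asks for a Grade 3 steroid taper of at least 4 to 6 weeks.

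**The concern.** The Grade 2 row sends a worsening participant to a row with fewer written restart conditions. Reaching Grade 1 does not imply that either missing condition is met. The grade labels in 5.2 rest on weakness, pain and daily activities, so a grade says nothing about CK. With a 1 mg/kg start and a taper of at least 4 to 6 weeks, weakness can also improve to Grade 1 while the dose is well above 10 mg/day.

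At stake is re-exposure of a participant whose muscle inflammation may still be active, or held down by steroid, after an event that 5.2 describes as potentially life-threatening when respiratory muscle or the heart is involved. This is a participant-safety point; the ORR analysis is not touched.

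**Working it through.** The plan gives no figure to reproduce. The check is a comparison of the text, followed by an illustration of size.

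**1. Which states after Grade 3 (no myocardial involvement) fall in the gap**

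| State when weakness is Grade 1 or less | Grade 2 restart rule | Grade 3 row as printed |
|---|---|---|
| Mild weakness, CK raised | Not met | Grade 1 row sends the case back to Grade 2 handling: no gap |
| (a) No weakness, CK raised | Not met | Hold released |
| (b) CK normal, prednisone above 10 mg/day | Not met | Hold released |
| CK normal, prednisone 10 mg/day or less | Met | Hold released: no gap |

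**2. Whether another printed rule closes (a) or (b)** (all Protocol)

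- Section 6.5.2 allows short-term systemic steroid for immune-related events.
- Section 6.8 makes failure to get down to 10 mg/day within 12 weeks a reason to stop. That is a stopping rule and sets no dose for an earlier restart.
- Section 6.8 also requires stopping for AST or ALT above 5 times ULN, with an exception for some participants who start with raised values. This may catch some raised-enzyme cases but is not a CK condition.
- Section 6.8 asks for Medical Monitor consultation once two or more doses are missed for an adverse event. With dosing every 2 weeks, a hold of 28 days or more always reaches that count (28/14 = 2), and a hold of 14 to 28 days misses one or two doses. Most Grade 3 holds will therefore reach the Medical Monitor, but no CK or steroid level is named.
- Section 7.1.2.1 requires full hematology and chemistry before reinitiation, but the Appendix 6 panel does not include CK.

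**3. Comparison within Appendix 5**

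| Section | Grade 2 steroid condition | Grade 3 |
|---|---|---|
| 2.2 Hepatitis | "temporarily and resume if recover to G1 or less on prednisone ≤ 10 mg/d" | Permanent stop |
| 10.1 Uveitis | "once corticosteroids for other concurrent systemic irAEs are reduced to ≤ 10 mg" | Permanent stop |
| 5.1 Arthritis | "and resume upon symptom control and on prednisone ≤ 10 mg/d" | "temporarily and may resume in consultation with rheumatology, if recover to G1 or less" |
| 5.3 Polymyalgia | "and resuming upon symptom control, prednisolone < 10 mg; if worsens, treat as per G3" | No ceiling, but restart tied to rheumatology |
| 5.2 Myositis | 10 mg, plus normal CK | No ceiling, no CK; referral asked for but restart not tied to it |

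Colitis (2.1) has a softer Grade 2 rule (taper first, or low dose), and its Grade 3 row also asks only for Grade 1 or less. The CK condition is specific to myositis.

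**4. Size of state (b)**

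From the Protocol: 1 mg/kg, a taper of at least 4 to 6 weeks (T = 28 to 42 days) and dosing every 14 days. Assumed: body weight 50 to 80 kg, so a starting dose D of 50 to 80 mg; a linear taper to zero; and the taper day G on which Grade 1 is reached.

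The dose stays above 10 mg until E = T × (1 − 10/D):

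- D = 50: 28 × 0.8 = 22.4 days; 42 × 0.8 = 33.6 days
- D = 80: 28 × 0.875 = 24.5 days; 42 × 0.875 = 36.75 days

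The window is L = max(0, E − G). It holds floor(L/14) or floor(L/14) + 1 infusions, or none if L = 0.

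| G (days) | L (days) | Infusions |
|---|---|---|
| 0 | 22.4 to 36.75 | 1 to 3 |
| 14 | 8.4 to 22.75 | 0 to 2 |
| 28 | 0 to 8.75 | 0 to 1 |
| 37 | 0 | 0 |

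A longer taper would lengthen the window. State (a) cannot be sized, because the documents give no time to CK recovery.

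**5. Participants affected**

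Assuming Grade 3 myositis without myocardial involvement in 0.2% to 1% of participants (not from the documents): 0.002 × 135 = 0.27 and 0.01 × 135 = 1.35.

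**The case against.** The strongest reply is that a restart after Grade 3 myositis is not unsupervised. Section 6.8 brings in the Medical Monitor for most such holds, the row asks for specialist referral, CK is listed for monitoring, and 5.2 warns about rechallenge. This stands, and it answers a reader who might infer that the plan leaves these restarts without oversight. It does not supply a criterion: none of these provisions says what CK or steroid dose is acceptable.

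A reader might also infer that the Grade 3 rule is looser in every respect. The documents do not support that. On symptoms, Grade 1 or less is at least as strict as symptom control, and the Grade 1 row recaptures mild weakness with raised CK. Only states (a) and (b) remain, and (a) is narrow.

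Nor is the missing steroid ceiling peculiar to myositis. The Grade 3 rows for arthritis, polymyalgia, colitis and immune thrombocytopenia also lack one. What sets myositis apart is that its Grade 2 row also requires normal CK, and its Grade 3 row neither carries that forward nor ties restart to the specialist.

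Three further points limit the claim. Appendix 5 is framed as recommendations, and Section 6.9.2 also points to outside guidelines not available here, so the finding concerns the printed text only. The instruction to treat a worsening case as Grade 3 can be read as escalating care without cancelling the Grade 2 restart conditions; a careful investigator may read it that way, but the Grade 3 row does not say so. Finally, SAP Section 6.1 restricts reporting to one analysis at a 15 February 2022 cutoff, and median treatment in the Phase I cohort was 9.6 weeks (Protocol Section 2.2). Few participants are likely to be on drug when a change takes effect, although Section 7.1.2.1 still allows reinitiation. This lowers the priority.

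**Conclusion.** The point holds as a low-priority alignment. Followed as printed, the myositis rows permit re-exposure after Grade 3 in two states in which they withhold it after Grade 2, and no other printed rule sets a CK or steroid level for restart.

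The expected number affected is about one participant or fewer, and lower still among those remaining on treatment. State (b) means about 0 to 3 infusions given earlier than the Grade 2 conditions would allow; state (a) is unsized. These figures rest on assumed incidence, body weight, taper shape and day of recovery. The textual finding rests on none of them, and it does not depend on how the possibly missing sign before 10 mg is read.

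**What to change.** In the Grade 3 part of the 5.2 row, state that restart requires all of: Grade 1 or less, normal CK, and prednisone (or equivalent) no more than 10 mg/day, in consultation with the rheumatologist or neurologist to whom the row already refers the participant. Leave the Grade 1, Grade 4, myocardial and rituximab rules as they are. Whether to carry the Grade 2 advice on objective findings into Grade 3 is for the sponsor to judge.

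The change is one sentence. CK is already listed for monitoring in 5.2, so no new test is needed. Protocol Appendix 2 requires IRB/IEC approval for amendments, so the sentence should travel with the next amendment and not prompt one of its own. The downside is a longer hold for the few participants concerned.
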